2.1 Background Information on Onchocerciasis

Onchocerciasis represents a major public health problem in affected countries with up to 1.34 million disability adjusted life years lost in 2017. This disproportionately high number is driven by disease-induced disability, and overall loss of economic productivity. The challenge for mass drug administration (MDA) programs is to eliminate transmission by periodic treatment of vulnerable populations with ivermectin. This removes microfilariae (mf) from the skin and temporarily prevents the release of mf by the adult female worm. However, mf return within 6-8 months, and control strategies delivering ivermectin on a six or 12 monthly cycle must be maintained over a 10 to 15-year period to reach elimination. Notably, MDA requires extensive logistical efforts and financial commitments. Treating entire populations requires ethical discussions and evaluations of cost-effectiveness. Success in MDA is dependent on the sustained coordination of supply logistics to ensure that treatment reaches all target recipients. Because of these challenges, interruption of transmission and disease elimination worldwide has proven more difficult than initially projected. In addition, MDA given for long periods carries the risk of resistance, described for ivermectin use in animal-health applications, together with sub-optimal response in humans.² Clearly other options are needed. According to a number of recent studies and simulations, 3-5 with the current strategies, elimination of onchocerciasis will not be feasible within the timelines of the United Nations Sustainable Development Goals, 6 i.e. 90% reduction in the number of people requiring intervention by 2030, or the previous goals set by the World Health Organization (WHO) to eliminate onchocerciasis in 80% of African countries by 2025.

New treatments are needed to improve individual clinical care for patients, reduce human suffering, achieve cure and ensure advancement toward the WHO's goal of elimination by providing additional tools to shorten the timelines for elimination.

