Ivermectin, the current treatment of onchocerciasis used in MDA programs, is microfilaricidal, killing only the larvae (mf). Although ivermectin is effective in reducing transmission cycles, therapy must be repeated at regular intervals (6 or 12 months) for 10-15 years, making implementation of a sustainable MDA program challenging and extremely difficult in some endemic countries. In addition, there are limitations with the use of ivermectin in zones where Loa loa is co-endemic. It has become clear that elimination may not be feasible by 2025 and success highly depends on local pre-control endemicity, past and future (therapeutic) coverage patterns, and geographic coverage. If MDA coverage is lower or the fraction of systematic nonadherers is higher than assumed in the simulations, the effectiveness of interventions will likely deviate from the model predictions and further delay the timeline to elimination. Recent modelling using ONCHOSIM predicts there will be around 10 million infected individuals with positive skin microfilaria in the areas covered by African Program for Onchocerciasis Control (APOC) in 2025,8 with > 6 million manifesting clinical symptoms.9 The total population at risk will be approximately 200 million in the countries formerly covered by APOC. Modelling activities have begun to assess the impact of a macrofilaricidal drug complementing or replacing current elimination activities. Preliminary results show that the timelines would shorten by 40-50% under both MDA and test-and-treat (TNT) strategies.

In summary, while MDA is effective in reducing transmission and morbidity in some settings, a drug that kills the adult worm or has a long-term inhibition of embryogenesis, offers the advantage of reducing the need for multiple cycles of MDA and would be an essential addition

to the global strategy to eliminate onchocerciasis. A new macrofilaricide or long-term treatment would be useful for:

- MDA, if the safety and tolerability profile and the duration of treatment are suitable, in order to drastically reduce the number of MDA cycles from 10-15 years as currently required.
- TNT strategies, for treatment of patients in endemic areas outside MDA campaigns when diagnostic tools are available, especially in "mop up" campaigns after the disease burden has been reduced by MDA programs rendering them no longer cost effective, or in areas where regular ivermectin distribution is difficult.

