- Arm K (n = 84): initial treatment with an active regimen selected from Part 1, followed by ivermectin at Month 6;
- Arm L (n = 84): initial treatment with the same active regimen selected from Part 1 as Arm K, followed by ivermectin matching placebo at Month 6;
- Arm M (n = 84): initial treatment with a second active regimen selected from Part 1, followed by either ivermectin or ivermectin matching placebo at Month 6 (decision to be made prior to Part 2);

• Arm N2 (n = 84): 7 days of ABBV-4083 400 mg plus appropriate duration of albendazole matching placebo and ABBV-4083 matching placebo followed by either ivermectin or ivermectin matching placebo at Month 6 (decision to be made prior to Part 2).

In the Alternate Scenario, a minimum of 84 subjects with two or more operable sites will be enrolled to allow for approximately 21 subjects per arm to undergo a single-site nodulectomy at Month 6 for the evaluation of *Wolbachia* depletion but still have remaining onchocercomata for evaluation of skin microfilariae and other endpoints at Month 24. The overall design for Part 2 Alternative Scenario is presented in Figure 3.

Post-Study IVM rescue **IVM** Rescue Arm K Arm B. C or D IVM N = 84Arm L Same as Arm K IVM-Pbo N = 84Arm M Arm B. C or D IVM or IVM-Pbo N=84 4083-Pbo x 7d Arm N2 IVM or IVM-Pbo N=84 Alb-Pbo x 7d D6 D13 Screen D0 **M3** M6 M12 M18 M24 Skin snip Skin snip Skin snip Skin snip Skin snip Nodulectomy Nodulectomy (subset) Skin snip (1° endpoint) (Combination rule endpoint)

Figure 3. Overall Design for Part 2 - Alternative Scenario

4083 = ABBV-4083; Alb = albendazole; d = days; D = (study) day; IVM = ivermectin; M = month; Pbo = placebo

Rescue treatment with ivermectin will be offered at the investigator discretion to subjects with clinically significant worsening of symptoms and / or signs related to onchocerciasis at any time during the study or to subjects with increased mean number of microfilariae in the skin at Month 18, compared to the mean number at Month 12.

Post-study ivermectin will be provided after nodulectomy at 24 months to any subject with positive skin and/or eye microfilariae.

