4.2 Secondary Objectives

4.2.1 Key Secondary Objectives for Part 2

The key secondary objectives for Part 2 are to determine:

- whether ABBV-4083 or ABBV-4083 + albendazole demonstrates a macrofilaricidal effect at 24 months;
- whether ABBV-4083 or ABBV-4083 + albendazole inhibits embryogenesis in adult female worms at 24 months.

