5.2 Secondary Efficacy Endpoints

5.2.1 Key Secondary Efficacy Endpoints in Part 2

The key secondary efficacy endpoints in Part 2 are:

- the proportion of live female adult worms per subject assessed by histological examination of all nodules collected after nodulectomy at Month 24;
- the proportion of live female adult worms with only degenerated embryos in uterus per subject as assessed by histological examination of nodules collected after nodulectomy at Month 24 out of all judgeable worms with embryos in uterus (normal or degenerated).

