8.3 Ivermectin: Rescue Medication, Post-Study, Screening Failures

Ivermectin used as described in this section for rescue medication or post-study will be provided as a single oral administration at the approved dose of 150 μ g/kg bw and is not an IMP, i.e. will not be presented as over-encapsulated tablets.

When ivermectin is administered at a follow-up or early termination visit, it must be administered only after completion of the procedures scheduled at that visit, and after confirmation of last menstrual period and a negative pregnancy test. Ivermectin will be administered to subjects under fasting conditions.

Subjects who fail screening in the communities or at the investigational centre will be referred to the National Program PNLMTN-CTP for MDA with ivermectin.

8.3.1 Rescue Medication in Part 1

In Part 1, ivermectin will be administered as rescue medication at any time during the study, at the investigator's discretion, to subjects with clinically significant worsening of symptoms and/or signs related to onchocerciasis.

8.3.2 Rescue Medication in Part 2

In Part 2, ivermectin will be proposed as rescue medication to all subjects with clinically significant worsening of symptoms and/or signs related to onchocerciasis at any time during the study and/or to subjects with increased mean number of skin microfilariae at Month 18, compared to the mean number at Month 12.

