If the primary hypothesis to satisfy the combination rule in Part 1 is not satisfied and ABBV-4083 + albendazole for 7 days (Arm C in Part 1) is to be carried forward to Part 2 (as either Arm K with ivermectin and Arm L without ivermectin, or as Arm M with or without ivermectin), an additional hypothesis using appropriate subjects from both Part 1 and Part 2 will be that more worms will have *Wolbachia* depletion at 6 months in subjects treated with ABBV-4083 + albendazole for 7 days (Arm C for Part 1 and Arm K plus Arm L [or alternately Arm M if appropriate] for Part 2) than in subjects treated with ABBV-4083 for 7 days (Arm A for Part 1 and Arm N2 for Part 2) among all subjects who completed treatment and who had live female worms from nodulectomies at 6 months.

In the case that ABBV-4083 for 7 days + albendazole for 3 days (Arm D in Part 1) is selected for Part 2 and ABBV-4083 + albendazole for 7 days (Arm C in Part 1) is not selected, and the primary hypotheses for satisfying the combination rule in Part 1 are not satisfied, then the arm or arms containing ABBV-4083 for 7 days + albendazole for 3 days will be treated as described elsewhere in this document for ABBV-4083 + albendazole for 7 days in the Alternate Scenario, and the data combined with Arm D in Part 1 for analysis.

10.1.3 Key Secondary Hypotheses in Part 2

The key secondary hypotheses in Part 2 are as follows:

- The first secondary hypotheses for Part 2 (Endpoint 2a) are that a smaller mean percentage of female adult worms per subject will be alive at 24 months among the subjects who completed treatment with one or more of three assigned regimens selected from Part 1 (Arms K, L and M) compared to either placebo (Arm N1) or ABBV-4083 for 7 days (Arm N2).
- The second secondary hypotheses for Part 2 (Endpoint 2b) are that a larger mean percentage of live female adult worms will have only degenerated embryos in their uteri

per subject at 24 months among the subjects who completed treatment with one or more of three regimens selected from Part 1 (Arms K, L and M) compared to either placebo (Arm N1) or ABBV-4083 for 7 days (Arm N2).

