10.4 Handling of Potential Intercurrent Events for the Primary and Key Secondary Endpoints

Subjects who do not complete the treatment as defined above will be excluded from the PP populations (but will be included in the ITT analyses). Subjects in Part 2 with evidence of reinfection will be included in all analyses as it is not possible to distinguish between reinfection and a failure in this study. However, in sensitivity analyses, those subjects will be excluded from efficacy analysis. Subjects in Part 2 who do not have skin snips at Month 24 will be excluded from the PP for microfilaria population, except those who received ivermectin rescue before Month 24. Any subject who received ivermectin rescue before Month 24 as allowed per protocol will be counted as a failure in both the PP and ITT analyses of the Part 2 primary and key secondary endpoints. Subjects who do not have nodulectomy data at Month 6 (for Part 1 and for Part 2 Alternate Scenario) or Month 24 (for Part 2) will be excluded from the PP for the ND6M or ND24M populations, respectively. Subjects who take prohibited medications (see Appendix 8-sections II and IV) will be excluded from the PP analyses; subjects who take medications with an anti-filarial or anti-Wolbachia effect at any time during the study (see Appendix 8 - Section II) will be counted as failures in the ITT analyses.

In the ITT analysis of the primary and key secondary endpoints, if the result is missing for the assessment, the assessment of that outcome will be a failure if the absence of data is due to administration of prohibited medication or withdrawal due to efficacy or safety issue. In the event of withdrawal of informed consent, subject lost to follow-up or withdrawal for a reason independent from the treatment (e.g. moving, lethal accident), multiple imputation will be used to impute the missing data.

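### Counting rescue ivermectin as failure on Month 24 worm survival (endpoint 2a) overrides valid histology, and would favour the drug if Arm N1 is rescued more often

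*Protocol*

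**What the plan says.** Section 10.4 applies one rule to rescue ivermectin before Month 24: the subject is "counted as a failure in both the PP and ITT analyses of the Part 2 primary and key secondary endpoints". It gives no numerical value for failure.

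Endpoint 2a (Section 5.2.1) is "the proportion of live female adult worms per subject assessed by histological examination of all nodules collected after nodulectomy at Month 24". The hypothesis in 10.1.3 is that "a smaller mean percentage of female adult worms per subject will be alive at 24 months" in Arms K, L and M than in the comparator. The objective it serves (4.2.1) is to determine "whether ABBV-4083 or ABBV-4083 + albendazole demonstrates a macrofilaricidal effect at 24 months". Section 10.6 tests it with a stratified Mann-Whitney test on the per-subject percentage.

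Section 2.1 states that ivermectin "is microfilaricidal, killing only the larvae (mf"). On the course after treatment it says: "However, mf return within 6-8 months".

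Rescue in Part 2 has two triggers. One is clinically significant worsening of onchocerciasis at any time. The other is a skin mf rise: Section 3.3 offers rescue to "subjects with increased mean number of microfilariae in the skin at Month 18, compared to the mean number at Month 12", and 8.3.2 repeats the trigger. Neither refers to adult worms.

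The per-protocol (PP) set for 2a (10.2) requires completed treatment, no prohibited medication and a Month 24 nodulectomy with female worms. Appendix 8, Section II exempts rescue ivermectin from the prohibited list, so rescued subjects who meet the other conditions stay in the set.

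**The concern.** For the skin mf primary endpoint, counting rescue as failure makes sense, because ivermectin directly clears what is being measured. Endpoint 2a measures something else. If ivermectin does not kill adult worms, a rescued subject's Month 24 worm viability is still a valid observation. The rule collects it and then replaces it.

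The replacement matters if rescue differs between arms. Failure on 2a means more live worms, so extra rescue in the comparator looks like worm killing by the drug. Several statements in the protocol make such a difference plausible in the Base Scenario:

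- Arm N1 receives placebo and then ivermectin at Month 6 (3.3). With mf returning after 6-8 months, that is about Months 12-14.
- Active regimens are expected to produce a slow decline in skin mf (2.4.3).
- Adult worm death is expected two years or more after treatment (2.4.2). A drug that clears skin mf with little worm killing by Month 24 is therefore a realistic case, and it is the case in which the rule misleads.

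No planned analysis would show this. The ITT analysis uses the same rule, and the only sensitivity analysis in 10.4 concerns reinfection. The SAP supplied covers Part 1 only. What is at stake is the macrofilaricidal conclusion. It could enter the Phase III recommendation if that recommendation is deferred to Month 24 (10.10).

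**Working it through.** **The plan's own figure.** The documents give no power or sample size for 2a. The Base Scenario primary comparison (10.3.2) supplies the sample size and alpha borrowed below: 70% v 30%, 62 v 31, two-sided alpha 0.017. With pooled variance:

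- pooled proportion = (62 × 0.70 + 31 × 0.30)/93 = 0.567
- null SE = √(0.567 × 0.433 × (1/62 + 1/31)) = 0.109
- alternative SE = √(0.21/62 + 0.21/31) = 0.101
- power = Φ((0.40 − 2.387 × 0.109)/0.101) = 91.7%, against 91% stated

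The figure reproduces.

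**Size of the shift.** Let v be the true share of worms alive, the same in both arms, and r an arm's rescue share. If failure is coded as 100% alive, the arm mean is r × 1 + (1 − r) × v = v + r(1 − v). The difference, active minus N1, is then (r_active − r_N1) × (1 − v). With v = 0.80:

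- 10% v 50% rescue: −0.40 × 0.20 = −8 percentage points
- 20% v 40%: −0.20 × 0.20 = −4 points
- 20% v 30%: −0.10 × 0.20 = −2 points

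All of this arises with no drug effect on worms.

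**Effect on the test.** This was simulated with no true effect.

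- From the protocol: the worm-count distribution in 10.3.1 (1 to 10 per subject), 62 v 31 subjects, two-sided alpha 0.017.
- Assumed: v; the rescue rates; failure = 100% alive; beta-binomial live/dead status with within-subject ICC 0.2 or 0.54 (10.3.1 uses 0.54, but for *Wolbachia* status); and that 0.017 and 62 v 31, which are primary-endpoint figures, also apply to 2a.

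Nominal false claims in the drug's favour are 0.017/2, about 0.8%. Unstratified Mann-Whitney, ranges over the two ICCs and repeat runs:

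| Rescue, active v N1 | Worms alive, both arms | False claims for the drug |
|---|---|---|
| 10% v 50% | 80% | 12-21% |
| 20% v 40% | 80% | 3-5% |
| 20% v 30% | 80% | 1-2% |
| 10% v 50% | 70% | 21-34% |
| 10% v 50% | 90% | 3-7% |

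Using observed histology instead gives 0.3-1.0%.

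**Sensitivity of the illustration** (80% alive unless stated).

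- Stratified rank test with four strata, as 10.6 specifies, ICC 0.2: 10% v 50% gives 18%, and 20% v 50% gives 10%.
- Failure ranked worse than every observed value, same stratified test: 81% and 51% for those two cases. The undefined failure value therefore matters a great deal.
- Equal rescue (30% v 30%), 50-80% alive: the two-sided rate is 1.2-2.0%, close to 1.7%. The bias comes from the difference in rescue between arms.
- Alpha for 2a at half of 0.017 (assumed): 10% v 50% gives about 6-13%.
- 45 v 22 evaluable subjects (assumed): 10% v 50% gives 7-15%.

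**The case against.** The strongest reply is that the size rests on inputs the documents do not supply. This is correct.

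- **Failure value.** Section 10.4 gives none, and the separate Part 2 SAP, which might, is not among the documents. Coding it as all worms alive is an assumption.
- **Rescue rates.** No section gives any. A reader might infer that a Month 12 to 18 rise is the established course in N1. The protocol says only that mf return within 6-8 months and gives no course after that, so a rise is plausible but inferred. A reader might also take the sample-size assumption that 70% of N1 is mf-positive at Month 24 as a rescue rate. It is a different event. If that 70% already counts rescue as failure, it is only a ceiling for N1 rescue.
- **Active arms are not alike.** Arm K, and possibly Arm M, also receive ivermectin at Month 6, so their Month 12 baseline may be low too.
- **Alpha and sample size.** Alpha for 2a follows the graphical procedure in Figure 6, which is not shown. The 2a set may be smaller than 62 v 31. Either could reduce the inflation.
- **Scope.** In the Alternative Scenario the comparator N2 is itself ABBV-4083, so the rescue imbalance is probably smaller. Endpoint 2a is secondary in a Phase II trial, and the Month 18 recommendation rests on safety and skin mf.
- **Composite strategy.** Counting rescue as failure is a recognised approach.

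These points limit the magnitude and the severity. They do not remove the mismatch. A composite on 2a mixes mf rebound into a measure of adult-worm survival, which is not what objective 4.2.1 asks. Nothing in the protocol exempts 2a, and the direction of the bias holds whenever N1 is rescued more often.

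**Conclusion.** The concern holds in a limited form. The text establishes that an undefined failure value is imposed on a per-subject percentage, and that it overrides histology which the protocol's own account of ivermectin leaves valid. The consequence is conditional: if rescue is more frequent in N1 than in an active arm, 2a is biased towards the drug with no effect on worm viability.

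Under the assumptions listed, with 80% of worms alive in both arms, false claims run from 1-2% (20% v 30% rescue) to 12-21% (10% v 50%), against about 0.8% nominal. These figures illustrate direction and possible size; they do not predict this trial. A reader might infer that a positive 2a result would be spurious, or that a large N1 excess of rescue is certain. The documents support neither, because they give no rescue rates and no failure value.

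Severity: should be fixed, mainly for the Base Scenario. The primary endpoint is not affected.

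**What to change.** In Section 10.4 and the Part 2 SAP:

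1. Restrict the rescue-equals-failure rule to the skin mf primary endpoint. It may also stay on endpoint 2b, since Section 2.4.2 says ivermectin sterilises worms temporarily; the failure value should then be stated.
2. For 2a, write: *observed Month 24 histology is used whether or not rescue ivermectin was given*.
3. Keep the failure version of 2a as a sensitivity analysis, with the failure value defined for a percentage.
4. Report rescue by arm, with its trigger.

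The rescue rule itself is unchanged. The passages on how rescue is given must, however, be reconciled, because they determine how many subjects are affected. Section 3.3 and footnote 18 of Table 8 describe an offer at the investigator's discretion. Section 8.3.2 says rescue will be proposed to all qualifying subjects. Section 3.5.3 says subjects with rising mf at Month 18 will receive it.

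The cost is about one sentence in the protocol, matching SAP text and one extra table. No new data are needed. The downside is that the 2a difference from N1 may look smaller.

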10.5 Population Level Summary and Analysis for the Primary Endpoints

The Part 1 primary and combination endpoints, the proportion of adult female worms without *Wolbachia* endobacteria assessed by immunohistology at 6 months, will be summarised among

the PP for ND6M population, and the odds ratio for each of the treatment arm comparisons of interest (Arm A vs E and Arm B vs E; Arm C vs E, Arm C vs A; Arm D vs E, Arm D vs A) will be calculated using contrasts within an alternating logistic regression model with treatment arm as factor and also accounting for within-subject correlation, each at 2-sided $\alpha = 0.10$.

The Part 2 primary endpoint of the percentage of subjects without skin microfilariae at Month 24 will be summarised across the PP for microfilariae population, and the adjusted odds ratio for each of the 3 active treatment arms will be compared to the comparator arm (Arm K vs N1 or N2, Arm L vs N1 or N2, and Arm M vs N1 or N2) using contrasts within a logistic regression model with treatment arm as factor and number of sites per subject (1, > 1) and mean baseline mf $(\le 5, > 5)$ as covariates at 2-sided $\alpha = 0.017$. Supportive subgroup analyses for the primary endpoint will also be performed for at least the following subgroups: number of sites per subject (1, > 1) and mean baseline mf $(\le 5, > 5)$.

The Part 2 combination rule endpoint for the alternate scenario, the proportion of adult female worms without *Wolbachia* endobacteria assessed by immunohistology at 6 months across all subjects treated with the same regimens in Parts 1 and 2 will be summarised among the PP for ND6M population, and the odds ratio for the comparison of interest (Arm K plus Arm L vs N2 [or Arm M vs Arm N2 if ABBV-4083 for 14 days is chosen for Arms K and L]) will be calculated using contrasts within an alternating logistic regression model with treatment arm as factor. P-values for the odds ratio of Part 1 and Part 2 will be combined using an inverse normal combination test and tested at 2-sided $\alpha = 0.10$.

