In order also to assess the effect of a dose of ivermectin at Month 6, participants will be randomised into four treatment arms, with the best candidate based on Part 1 results administered with ivermectin and with ivermectin placebo at Month 6.

Within each treatment arm, subjects will be stratified by the number of operable sites with onchocercomata and by mean screening skin mf. There will be four strata, i.e. 1 site and less than or equal to 5 mf/mg, more than 1 site and less than or equal to 5 mf/mg, 1 site and more than 5 mf/mg, more than 1 site and more than 5 mf/mg.

A total of either 294 subjects (Base Scenario) or 336 subjects (Alternative Scenario) will be recruited. The Base Scenario will be employed:

- if neither Arm C nor Arm D from Part 1 is selected for continued enrolment in Part 2, or
- if either Arm C and/or Arm D in Part 1 is selected for continued enrolment in Part 2 and Arm C and/or Arm D has demonstrated superiority over both Arm E and Arm A in Part 1.

[figure not shown]
The Alternative Scenario will be employed if either Arm C and/or Arm D in Part 1 is selected for continued enrolment in Part 2, but Arm C or Arm D in Part 1 has not demonstrated statistical superiority over both Arm E and Arm A.

In the Base Scenario, subjects will be randomised continuously 2:2:2:1 into one of four parallel treatment arms until group size is achieved:

- Arm K (n = 84): initial treatment with an active regimen selected from Part 1, followed by ivermectin at Month 6;
- Arm L (n = 84): initial treatment with the same active regimen selected from Part 1 as Arm K, followed by ivermectin matching placebo at Month 6;
- Arm M (n = 84): initial treatment with a second active regimen selected from Part 1, followed by either ivermectin or ivermectin matching placebo at Month 6 (decision to be made prior to Part 2);
- Arm N1 (n = 42): initial treatment with ABBV-4083 matching placebo and albendazole matching placebo, followed by ivermectin at Month 6.

Details of timing and sequence of investigations and measures are provided in the Schedule of Events (see Appendix 2). The overall design for Part 2 Base Scenario is presented in Figure 2.

Figure 2. Overall Design for Part 2 - Base Scenario

4083 = ABBV-4083; Alb = albendazole; d = days; D = (study) day; IVM = ivermectin; M = month; Pbo = placebo

In the Alternate Scenario, subjects will be randomised continuously 1:1:1:1 into one of four parallel treatment arms until group size is achieved:

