For the Part 2 primary hypothesis in the Base Scenario that compares the proportion of subjects without skin microfilariae at Month 24 between an active arm (Arm K, L or M) and the placebo arm (Arm N1), 62 subjects in the active arm and 31 subjects in the placebo arm will provide 91% power to detect the difference between an active arm (Arm K, L or M) where 70% of subjects are without skin microfilariae at Month 24 and the placebo arm (Arm N1) where 30% of subjects are without microfilariae at Month 24, using a logistic regression with 2-sided α =0.017. In addition, 62 subjects per arm will provide 80% power to detect the difference between two active arms where 90% and 70% of subjects are without skin microfilariae at Month 24, respectively, using a logistic regression with nominal 2-sided α =0.05. Assuming a 25% drop-out rate by Month 24, 84 subjects in each active arm and 42 subjects in the placebo arm are planned to be enrolled.

For the Part 2 primary hypothesis in the Alternate Scenario that compares the proportion of subjects without skin microfilariae at Month 24 between each active arm (Arm K, L or M) and the control arm (Arm N2: 7 days of ABBV-4083), 62 subjects per arm will provide 84% power to detect the difference between an active arm (Arm K, L or M) where 90% of subjects are without skin microfilariae at Month 24 and the control arm (Arm N2) where 65% of subjects are without microfilariae at Month 24, using a logistic regression with 2-sided α =0.017.

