10.7 Multiplicity Adjustment

Since Part 1 is a Phase-II proof-of-concept study, no adjustment will be made for the multiple comparisons in the primary endpoint (Arm A vs Arm E, Arm B vs Arm E, Arm C vs Arm A, Arm C vs Arm E, Arm D vs Arm A and Arm D vs Arm E). Each comparison will be controlled at 2-sided $\alpha = 0.10$.

In Part 2, the multiplicity adjustment to control the overall Type I error rate at 5% will include: (1) Bonferroni allocation of $\alpha = 0.017$ to each primary endpoint comparison: Arm K vs Arm N1, Arm L vs Arm N1, and Arm M vs N1; (2) a graphical approach to multiplicity adjustment to control the family-wise error at 0.05 (see Figure 6). The same method will be used in the Part 2 Alternate Scenario, with comparisons between Arms K-M and Arm N2.

[figure not shown]

Figure 6. Graphical Approach to Multiplicity Control in Part 2

Of note, the parallel graphical approach above shows how the α is passed to the next comparison if the null hypothesis is rejected.⁸¹

In the Alternate Scenario of Part 2, the primary endpoint for satisfying the combination rule in Part 1 continued in Part 2 (combination rule endpoint) is conducted at 2-sided $\alpha = 0.10$ with no need to adjust for multiplicity per Section 5.5.2 of the European Medicines Agency Guideline on Multiplicity Issues for Clinical Trials.⁸²

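### Part 2 primary model: adding continuous log baseline skin mf density beside the two stratification factors is an optional, small gain in power, not the correction of an error

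*Protocol*

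**What the plan says.** Protocol 10.5 defines the Part 2 primary analysis as a logistic regression of clearance of skin mf at Month 24. Treatment arm is the factor, and the covariates are "number of sites per subject (1, > 1) and mean baseline mf", with mf in two levels (at most 5, above 5). Each of the three comparisons with control is tested at 2-sided 0.017. No continuous mf term is given.

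The two covariates are the Part 2 randomisation factors. Protocol 3.3 says that "subjects will be stratified by the number of operable sites with onchocercomata and by mean screening skin mf", and its four strata start with "1 site and less than or equal to 5 mf/mg, more than 1 site and less than or equal to 5 mf/mg". Protocol 7.3.2.1 repeats the cut, and Protocol 10.6 uses the same strata for the tests of key secondary endpoints 2a and 2b.

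Density itself is a continuous measurement. Four snips are taken, weighed and counted (Protocol 9.3.3.1.2), and the result is expressed as mean mf per mg (Protocol 5.2.2). Entry requires mf on at least 2 of 4 snips (Protocol 6.1), and the exclusion criteria in Protocol 6.2 set no upper limit on skin density, so the upper stratum is open-ended.

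The supplied SAP covers Part 1 only (SAP 1.0). Its exploratory subgroup models include baseline skin mf density and use its continuous value (SAP 9.6). The Part 2 SAP is a separate document and was not available.

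**The concern.** Splitting a continuous baseline measure in two treats every subject above 5 mf/mg as having the same expected outcome, and likewise every subject at or below it. If density matters within those halves, the model ignores information that the trial already collects.

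Such a relation is plausible. The endpoint is absence of the same parasite stage in the same tissue, and the protocol expects active treatment to lower skin mf slowly (Protocol 2.4.2 and 2.4.3). The starting level could therefore affect who reaches zero by Month 24.

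At stake is a small amount of power in the three primary comparisons. It matters most in the Alternate Scenario, which is planned at 84% power and 2-sided 0.017. Validity and the type I error rate are not in question.

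**Working it through.** **1. The plan's own figures.** Protocol 10.3.2 states for the Base Scenario that "62 subjects in the active arm and 31 subjects in the placebo arm will provide 91% power to detect the difference", at rates of 70% v 30% and 2-sided alpha 0.017 (critical value 2.387). The two-proportion formula is

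power = Φ[(|p1 − p2| − z·SE0) / SE1], with SE0 pooled and SE1 unpooled.

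- Base: pooled rate = (62×0.7 + 31×0.3)/93 = 0.567. SE0 = √[0.567×0.433×(1/62 + 1/31)] = 0.1090. SE1 = √[0.21×(1/62 + 1/31)] = 0.1008. Power = Φ[(0.40 − 2.387×0.1090)/0.1008] = Φ(1.39) = 91.7%. Exact enumeration of the unadjusted logistic Wald test gives 90.7%, and of the likelihood ratio test 91.1%. Stated: 91%.
- Alternate (62 v 62, 90% v 65%): SE0 = √(0.775×0.225×2/62) = 0.0750. SE1 = √[(0.09 + 0.2275)/62] = 0.0716. Power = Φ[(0.25 − 2.387×0.0750)/0.0716] = Φ(0.99) = 83.9%. The exact Wald figure is 84.2%. Stated: 84%.

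Both figures reproduce with no covariate, so neither depends on how baseline mf is coded.

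**2. What has to be assumed.** The documents give no prognostic strength for baseline mf, no shape for the relation, and no share of subjects at or below 5 mf/mg. The simulations assume normally distributed log density, randomisation balanced on the cut, and odds of clearance that fall by a fixed odds ratio (OR) per SD of log density. The number-of-sites covariate was left out.

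**3. Replacing the stratum term by log density.** 10,000 trials per setting, with a share at or below the cut of 30%, 50% or 70%. The Monte Carlo standard error near 92% is √(0.92×0.08/10,000) = 0.27 points. All models were fitted to the same simulated data. Gains are in percentage points, compared share by share.

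| OR per SD | Base: two-level | Base: continuous | Gain | Alternate: two-level | Alternate: continuous | Gain |
|---|---|---|---|---|---|---|
| 1 | 90.7–91.2% | 90.7–91.3% | 0.0 to 0.1 | 84.1–84.4% | 83.5–84.0% | −0.6 to −0.4 |
| 1.5 | 91.5–91.7% | 91.8–92.1% | 0.3 to 0.4 | 84.2–85.2% | 84.6–85.3% | 0.1 to 0.6 |
| 2 | 92.3–92.6% | 93.3–93.6% | 0.7 to 1.1 | 85.0–86.0% | 86.7–86.8% | 0.8 to 1.7 |
| 3 | 93.5–94.5% | 95.4–96.0% | 1.5 to 1.9 | 86.4–88.7% | 89.7–90.3% | 1.6 to 3.8 |
| 4 | 94.4–95.4% | 97.0–97.2% | 1.8 to 2.6 | 86.6–90.2% | 91.5–92.3% | 2.1 to 4.9 |

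If the true effect is instead a step at the cut (step OR 4, Base, 50% share), replacement does worse: 92.2% against 93.2%, a loss of 1.0 point.

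**4. Keeping the stratum term and adding log density.** 4,000 trials per setting, share 30% or 50%. The standard error near 87% is √(0.87×0.13/4,000) = 0.53 points.

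| Setting | Stratum only | Log density only | Both |
|---|---|---|---|
| Base, OR 2 | 92.2–93.0% | 93.3–93.9% | 93.2–93.6% |
| Base, OR 3 | 93.7–93.8% | 95.4–95.9% | 95.2–95.6% |
| Alternate, OR 2 | 86.1–86.4% | 87.1–87.6% | 87.2–87.5% |
| Alternate, OR 3 | 86.7–87.5% | 89.9–90.2% | 89.8–90.0% |
| Base, step OR 4 | 92.8–93.6% | 92.6–92.7% | 92.9–93.6% |
| Alternate, step OR 4 | 85.4–87.0% | 84.5–86.1% | 85.0–86.8% |

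With no effect of density, the three models lie within 0.6 points of each other. A further run (3,000 trials, 50% share) gave, for stratum only against both, 94.7% to 96.1% (Base, OR 3, gain 1.4 points) and 87.0% to 89.5% (Alternate, OR 3, gain 2.5 points).

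Using both terms keeps nearly all of the gain and removes most of the step-effect loss. What remains is at most 0.4 points, within simulation error.

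**The case against.** The case for leaving the model alone is good, and most of it stands.

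- **The coding is deliberate.** Adjusting for the factors used in randomisation is conventional, and the key secondary tests use the same strata. A reader might infer that the two-level term is a mistake, or should give way to a continuous one. The documents do not support that. Dropping it would remove a randomisation factor from the model and would lose about 1 point of power if the effect is a step. This objection disposes of replacement, but not of adding a term.
- **The strength is unknown.** A reader might also infer that baseline density is the strongest predictor of clearance. No passage says so. The shape is doubtful too: ABBV-4083 acts by sterilising adult worms, whereas Arms K and N1 also receive ivermectin at Month 6, which removes skin mf directly. One log-linear slope need not fit all arms.
- **Nothing stated is wrong.** It would be wrong to conclude that the trial is underpowered. Both power figures reproduce without covariates, and in the log-linear settings above the planned two-level model gives about the planned power or more.
- **No bias is involved.** Imbalance in density within a stratum is chance imbalance under randomisation, not systematic error in the odds ratio.
- **The plain logarithm has a gap.** The per-protocol population must be mf-positive at baseline (Protocol 10.2), but the ITT population need not be. Screening snips are repeated when more than 30 days old (Protocol Table 8), so an ITT subject could have a baseline of zero. Any log term needs an offset.
- **The Part 2 SAP has not been seen.** It may already plan such an analysis.

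**Conclusion.** This is an optional efficiency improvement. The planned model is valid, and no stated sample size, power or alpha changes. What holds is narrow: the primary model uses baseline density only through the randomisation cut, so variation within strata is unused.

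Adding log density beside both stratification factors would gain about 0 points if density is not prognostic (a few tenths either way in the simulations). The gain would be about 1 to 1.5 points at OR 2 per SD, and about 1.5 to 3 points at OR 3 per SD, with the larger gains in the Alternate Scenario. There is no material loss if the true effect is a step at the cut.

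These sizes rest on an assumed prognostic strength, a log-linear effect common to all arms, and assumed shares at or below 5 mf/mg. They were obtained with log density itself. The version with an offset was not simulated, because the documents give no density distribution.

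**What to change.** In Protocol 10.5 and the Part 2 SAP, keep number of sites (1, >1) and baseline mf (≤5, >5) in the primary logistic model and add continuous log baseline density. One workable form is log(density + 1), which is defined for a zero baseline in the ITT analysis. Prespecify it before unblinding. If the sponsor prefers to leave the primary model as it is, the same model can serve as a prespecified sensitivity analysis. Leave the randomisation strata, the subgroup tables and the stratified tests in Protocol 10.6 unchanged.

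The cost is one extra parameter. No change to sample size, randomisation or data collection is needed. The report should state that the odds ratio is then conditional on density as well as on the strata, so it is not directly comparable with one from the two-factor model.
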